Individual characteristics may determine if E2 has a beneficial or worsening effect, which could also account for inconsistencies observed in the direction of the effect of E2 on reward-motivated behaviors such as binge eating. Specifically, dopamine has an established effect on multiple aspects of reward^{22, 23, 44, 58} and there is evidence that the effect of E2 may be dopamine activity dependent.⁵⁹⁻⁶³ Preclinical studies established that E2 enhances dopamine activity,⁶⁴⁻⁶⁶ but at its highest levels E2 may inhibit dopamine.²³ Also, dopamine appears to have an inverted U effect: an optimal amount of dopamine results in maximal function whereas insufficient or excessive levels lead to dysfunction,^{58, 67, 68} suggesting that the effect of E2 on dopamine [reward] motivated behaviors depends on baseline dopamine.^{23, 46, 60, 69} Specifically, E2 is beneficial for subgroups with *lower* baseline dopamine (enhancing activity to the optimal level) and worsening for subgroups with higher baseline dopamine (leading to an excessive amount of dopamine). Corroborating this, the beneficial effect of E2 on delay discounting is driven by *COMT* genotype, which is often used as a proxy for baseline dopamine activity: declines in delay discounting during high E2 were observed among *COMT* Val allele carriers,³² the allele associated with less dopamine activity. This is highly relevant for BN:^{70, 71} BN is associated with decreased dopamine activity,⁷²⁻⁷⁴ reduced brain activation in dopamine-related reward pathways,^{27, 75} and possibly a higher frequency of gene alleles associated with decreased dopamine;^{71, 76} though this is inconsistent,⁷⁷ unconfirmed by genome-wide studies, and perhaps an indirect and/or interactive association.⁷⁸⁻⁸⁰ Thus, because women with BN represent a subgroup of the population with low dopamine activity, low E2 may detrimentally affect the reward

response and further promote reward-motivated behavior via dopamine withdrawal, whereas high E2 is beneficial by enhancing dopamine activity to an optimal level, in turn decreasing the reward response and reward behaviors.

Together, we hypothesize women with BN are a hormone sensitive phenotype with precursory impaired dopamine activity, leading to increased reward response (e.g., reward-related inhibitory control deficits, heightened reward sensitivity, impaired delay discounting) and therefore, increased engagement in reward-motivated

[figure not shown]

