The objective of this proposal is to examine the direct and mechanistic role of ovarian hormones on binge eating in women with BN ($n = 15$). Our overarching hypothesis is that BN represents a hormone sensitive phenotype and this sensitivity is modulated by E2's effects on aspects of the reward response such that reward-motivated behaviors increase in the context of low E2. For the first time in humans, we propose an experimental design that parallels animal models to directly manipulate ovarian hormones: temporarily stopping the menstrual cycle using a GnRH agonist and addback E2 and P4 independently in a double-blind crossover design. This utilizes an established design developed to determine the hormonal triggers of premenstrual dysphoric disorder PMDD and depression.⁸⁷⁻⁸⁹ We propose this proof-of-concept study to obtain empirical evidence supporting our overarching hypothesis and the utility of this experimental design in a BN population. The experimental design proposed here is the only way to confidently explore the direct impact of ovarian hormones on binge eating in BN. Observational designs provide insight but cannot quantify the mechanism in which ovarian hormones impact binge eating. Further, the impact of E2 on neurocircuitry contributing to BN has been deprioritized by research to date.²⁵ Successful completion of the proposed aims will provide guidance in regard to if (and how) E2 and P4 directly affect binge eating in BN. This will not only provide the empirical direction needed for the investigators to complete larger, *hypothesis-driven* mechanistic trials, but will provide direction for future research addressing neuroendocrine, neurobiological, and brain activity and function in BN.

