| Scoring for Primary Outcome Self-Report Questionnaires | | | |
|--|--------------|---------------|---------------|
| Scale | Likert Scale | Minimum Score | Maximum Score |
| EPSI | 5 point | | |
| Binge eating | | 0 | 32 |
| BIS/BAS | 4 point | | |
| Behavioral inhibition | | 7 | 28 |
| Fun seeking | | 4 | 16 |
| Reward responsiveness | | 5 | 20 |
| SPSRQ | 2 point(T/F) | | |
| Sensitivity to reward | | 0 | 24 |

Reward Response Behavioral Tasks

- a) **Monetary Incentive Delay Task (MIDT)**¹⁷⁴: Two event-related MID runs consist of 6-second trials during which women will be presented with a cue shape, a fixation crosshair (for variable duration), the target, and performance (win/loss/neutral) feedback. Cues indicate whether it is an incentive (gain, loss) or non-incentive trial. In incentive trials, women can gain or lose money by pressing a button during target presentation; difficulty is based on individual reaction times. MID defines reward response as the average speed of responses to reward vs. non-reward trials during a reward task.
- b) **Delayed Discounting (DD) Task**: The DD task¹⁹² is used to understand how subjects make a choice between an immediate, smaller reward and a larger reward given after a time delay. Discounting is assessed across 4 time delays: 2, 30, 180, and 365 days later. Delays are presented in a mixed fashion. Questions are posed to participants asking whether they would prefer to receive a given amount of money immediately or a larger amount after a delay. The amount of money available immediately is adjusted with each trial to calculate an indifference point for each delay periods. Discounting rates of hypothetical and real reward tasks are comparable.¹⁹³⁻¹⁹⁵ DD defines reward response as the tendency to choose small, immediate rewards over larger, delayed rewards. The task determines the rate of devaluation over time for the larger, delayed reward, which is defined as the indifference point.¹⁹² The k parameter will be obtained and used as the primary outcome.
- c) **Go No/Go Task**: A behavioral Go No/Go Task will be used as a measure of inhibitory control. Each trial consists of one stimulus indicating either “go” (response) or “no/go” (do not respond). The response accuracy of each no/go trial is used as the indicator for inhibitory control such that fewer errors (“go” response on a “no/go” trial) signifies better inhibitor control.

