7.2 Statistical Methods

Statistical analyses are completed using the most recent version of R. Primary outcome measures, as described below, are binge eating and aspects of the reward response. Methods are modeled after similar, successfully implemented studies.^{87, 117} All measures included are empirically valid, and well-established, thus, measures will be scored according to standard conventions and scoring procedures. Descriptive statistics and graphics will be used to screen for errors, outliers, and potential influential observations and to check distributional assumptions. Where appropriate statistical estimates will be tabulated. We first complete analysis without covariates. As appropriate, relevant covariates may also be included in data analysis (e.g., negative affect, self-reported food intake).

PRIMARY OUTCOMES

Binge eating will be defined as: 1) the EPSI subscale binge eating score obtained at each study visit (T1-T4), which represents a continuous score of symptoms over the previous week (higher scores indicate more symptoms); 2) a weekly average based on daily frequency obtained from the DSRP. For both the subscale score and weekly average, the primary outcome is the last week of each phase of the hormone challenge to capture the period of time with maximal symptom change.

Reward response will be defined by the Monetary Incentive Delay (MID),¹⁷⁴ the Delayed Discounting (DD), and Go No/Go behavioral tasks and the BIS/BAS and SPSRQ self-report questionnaires. MID operationalizes reward response as *motivated behavior*: the average speed of responses to reward vs. non-reward trials during a reward task.

DD operationalizes reward response as “delay gratification”: the tendency to choose small, immediate rewards over larger, delayed rewards. The task determines the rate of devaluation over time for the larger, delayed reward, which is defined as the k parameter. We use behavioral tasks of monetary reward vs. food because the value of food is dependent on hunger state^{202, 203} and it reduces the confounding effect of the task provoking symptoms.³⁴

The Go/No Go Task is a behavioral measure of inhibitory control. Inhibitory control is defined by the response accuracy of the go no/go trials with fewer errors (“go” response on a “no/go” trial) indicating better inhibitory control.

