The BIS/BAS and SPSRQ will be included as a self-report measures of reward response. Specifically, we will include the reward responsiveness, behavioral inhibition, and fun seeking subscales of the BIS/BAS as self-report correlates of the reward response. The SPSRQ will be used to assess sensitivity to reward.

Hypothesis. Our overarching hypothesis for the following aims is that BN represents a hormone sensitive phenotype and this sensitivity is displayed as an impaired reward response within the context of low E2 such that E2 addback will be beneficial for all outcomes of interest (i.e., binge eating, aspects of the reward response). As such, our null hypothesis is that there is no effect of E2 on binge eating or the reward response. For all hypothesis tests, we will use the Benjamini-Hochberg Procedure to correct for multiple comparisons.

Aim 1: Quantify the direct effect of E2 and P4 on binge eating in women with BN.

Dependent variables: EPSI binge eating subscale score; DSRP binge eating weekly average.

Independent variables: Treatment sequence, treatment condition, and selected covariates

The two longitudinal measures of binge eating (i.e., EPSI subscale score and DSRP weekly average) will be fit to linear mixed effect models with subject-specific random intercept assuming an unstructured covariance among different time points. Such a covariance allows different variance and covariance parameters to be estimated for each time point allowing for potential increasing or decreasing variability in outcomes during each of the follow-up time points for each outcome and will include fixed effect predictors such as binary treatment sequence (E2-P4 or P4-E2) and treatment condition of categorical variable with three levels: Lupron-alone, E2, or P4, where effect size and standard error of fixed effect parameters will be estimated in the described model followed by t -test. Study hypotheses comparing outcomes between group outcomes of E2 vs. Lupron-alone, E2 vs. P4, and P4 vs. Lupron-alone, will be tested using contrasts test through t -test of least squares means estimate in the context of the main effects model.

Along with the primary contrasts of interest described above, additional contrasts between each end point of treatment condition (Lupron-alone, E2, or P2) and baseline (T1), which occurs prior to medication administration, will be tested using the statistical model just described above.

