Aim 2: Determine the effect of E2 on reward response and related correlates (e.g., behavioral inhibition) in women with BN.

Dependent variables: Behavioral measures of reward response, self-report measures of reward response.

Independent variables: Treatment sequence, treatment condition, and selected covariates

Behavioral measures of reward response (MID, DD) and related correlates (Go No/Go, BIS/BAS, SPSRQ) will be fit to linear mixed effect models as described above with binary treatment sequence (E2-P4 or P4-E2), treatment condition, and covariates as independent variables and reward response as dependent variables. The contrasts between E2 and baseline (T1) or Lupron-alone (T2) will be tested in the same model.

For the behavioral tasks, beneficial impacts of E2 are defined as an accelerated speed of response to rewards and improvement in reward learning during the MID, higher indifference points during the DD task, and fewer errors on the Go No/Go Task. For self-report questionnaires, a decrease in scores represents a beneficial response as higher scores indicate more “pathological” responses.

Aim 3: Examine the association between reward response (defined in Aim 2) and binge eating before and after E2 addback.

Null hypothesis: There is no association between reward response and binge eating before and after E2 addback
Alternative hypothesis: There is an association between reward response and binge eating before and after E2 addback.

We will explore Pearson correlations between change in self-reported reward responses and change in binge eating between baseline and E2 addback. Binge eating will be defined by the EPSI subscale score. Reward response will include the BIS/BAS reward responsiveness subscale, and SPSRQ reward sensitivity subscale. Specifically, a change score will be created that signifies the amount and direction of change that occurred in binge eating and reward responses between baseline and E2 addback for each subject. A Pearson correlation will then be examined between binge eating and reward response change scores.

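### Aim 2's benefit rule for the MID conflicts with the direction implied by the study's own model and with the self-report reward scales beside it, and the exception is not explained

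*Combined protocol and SAP*

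**What the plan says.** Section 7.2, Aim 2, fixes what will count as benefit. For the MID, "beneficial impacts of E2 are defined as an accelerated speed of response to rewards and improvement in reward learning during the MID". For the questionnaires, in the same paragraph, "a decrease in scores represents a beneficial response". The section lists those scales as the "reward responsiveness, behavioral inhibition, and fun seeking subscales of the BIS/BAS as self-report correlates of the reward response", plus the sensitivity-to-reward scale of the SPSRQ. Its hypothesis is that "E2 addback will be beneficial for all outcomes of interest".

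The MID outcome is defined three times. Sections 3.2 and 7.2 treat it as a measure of motivated behavior, taken as "the average speed of responses to reward vs. non-reward trials during a reward task". Section 6 agrees: "MID defines reward response as the average speed of responses to reward vs. non-reward trials during a reward task".

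The model is in section 1.1. It describes bulimia nervosa as involving a raised reward response and states that "high E2 is beneficial by enhancing dopamine activity to an optimal level, in turn decreasing the reward response and reward behaviors". The overarching hypothesis in the same section is that "reward-motivated behaviors increase in the context of low E2".

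**The concern.** If reward response on the MID is the speed advantage on reward trials, a larger advantage is a larger reward response. A model in which E2 helps by lowering the reward response then predicts a smaller advantage under E2. Aim 2 scores faster responding to reward as the benefit.

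The MID is a designated primary outcome. With two directions on file, a significant slowing on reward trials relative to non-reward trials could be reported as failure under Aim 2 or as confirmation under section 1.1, and the reverse holds for a significant acceleration. The mediation analysis in section 7.2 depends on Aims 1 and 2 being supported and uses reward-motivated behavior as the mediator. If the MID enters it, the expected sign of that path is also unclear. Aim 3 uses only self-report reward scales and is not affected.

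There is a second gap in the same sentence: it speaks of response to rewards and leaves out the non-reward comparison that is part of the defined outcome.

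**Working it through.** **Directions side by side**

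| Source | Measure | Direction counted as E2 benefit |
|---|---|---|
| Section 1.1, model | Reward response in general | Decrease |
| Section 1.1, overarching hypothesis | Reward-motivated behavior | Decrease (it rises when E2 is low) |
| Section 7.2, Aim 2 | BIS/BAS reward responsiveness | Decrease |
| Section 7.2, Aim 2 | BIS/BAS fun seeking | Decrease |
| Section 7.2, Aim 2 | SPSRQ sensitivity to reward | Decrease |
| Section 7.2, Aim 2 | MID speed of response to reward | Increase |

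The Aim 2 directions for delay discounting (higher indifference points) and Go/No-Go (fewer errors) agree with the model.

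**Counts.** Aim 2 outcomes are the MID (taking one summary variable), delay-discounting k, Go/No-Go, BIS/BAS reward responsiveness, behavioral inhibition and fun seeking, and SPSRQ reward: 7. Each has two E2 contrasts, against T1 and against T2: 7 × 2 = 14, of which 1 × 2 = 2 are on the MID. Four of the outcomes measure strength of reward response: 3 score a decrease as benefit and 1, the MID, an increase. Behavioral inhibition falls under the questionnaire rule but is not a reward-strength scale, so it is left out of the four. Section 6 names behavioral activation in its list of primary BIS/BAS outcomes where the scoring table and section 7.2 name fun seeking; that swap leaves the counts unchanged.

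**Power does not depend on the label.** Section 7.1 gives a detectable effect of 0.77 for n = 15, two-sided 0.05, 80% power. A paired t-test has df = 14 and noncentrality 0.77 × √15 = 2.98, giving power of 79.2% (exact detectable effect 0.778). The plan's figure is reproduced. Splitting the rejection probability by sign, without the planned Benjamini-Hochberg correction:

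| Assumed true effect (standardized) | Reject in the true direction | Reject in the opposite direction |
|---|---|---|
| 0.5 | 0.438 | 0.00008 |
| 0.77 | 0.792 | about 0.000001 |
| 1.0 | 0.949 | about 0.00000001 |

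Reversing the sign of the effect swaps the two columns and leaves the total unchanged. A significant MID result will therefore almost always show the true sign; the open question is which sign the plan calls benefit.

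**The missing comparator.** Let C = response time on reward trials minus response time on non-reward trials. If responding quickens by the same amount x on both, the change in C is −x − (−x) = 0, yet response to reward is faster by x and meets the wording of Aim 2. Table 4 in section 6 repeats the MID at T1 to T4, and T1 and T2 come before E2 in every participant. If speed improves with repetition (an assumption), reward-trial speed would improve from T1 or T2 to the E2 visit with no E2 effect.

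**The case against.** The strongest reply is that acceleration may be what the investigators intend.

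- The hypothesis in section 7.2 calls the reward response under low E2 impaired, without a sign, and faster responding could be read as less impairment.
- Section 1.1 says dopamine has an optimal level at which function is greatest, that women with bulimia nervosa sit below it, and that E2 raises it. Quicker incentive responding could be restored function.
- The same section cites a finding of lower reward responsivity when E2 is suppressed. It also says the direction of E2 effects partly depends on the aspect of reward, with choice measures more consistently inverse than action measures. The MID measures action.
- Section 1.1 mostly illustrates reward-motivated behavior by binge eating, not task speed.
- The reward-strength grouping is an interpretation, since Aim 2 gives one blanket direction for all questionnaires.

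This stands to the extent that the MID direction implied by section 1.1 is an inference: no text available for review, apart from Aim 2, states a direction for the MID. The text between sections 1.5 and 3.1, and Figure 1, were not available. But none of the texts listed names the MID or gives a reason to exempt it. Section 1.1 also resolves the mixed directions by placing this population in the low-dopamine group, and concludes that E2 lowers the reward response.

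The comparator may be omitted only as shorthand, since three sections define it. That is reasonable, but the rule that will be applied should say so.

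A reader might infer that the Aim 2 direction is simply reversed by mistake, or that about 79% of such trials would be mislabelled. The documents support neither. The first is not settled, for the reasons above. The second assumes that section 1.1 gives the right MID direction and that the true effect equals the detectable 0.77; the plan predicts no effect size for the MID.

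**Conclusion.** The concern holds as an unreconciled conflict. The Aim 2 rule for the MID runs against the direction implied by section 1.1 combined with the plan's MID definition, and against three self-report reward scales in the same paragraph. No available text justifies the exception.

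The effect is on interpretation only. Estimates, intervals, p-values and power that change: none. The benefit label is in doubt for 1 of 7 Aim 2 outcomes and 2 of 14 E2 contrasts, and with it whether the MID supports the claim of benefit on every outcome. In a 15-participant pilot meant to guide larger trials, that is worth settling beforehand, but it does not threaten the analysis itself. Confidence is medium, because the conflict rests on combining sections and some text and a figure could not be seen. The practice-speeding risk further assumes that responses quicken with repetition.

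**What to change.** Before unblinding, amend Aim 2 in section 7.2:

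1. State the MID benefit rule on the defined contrast, response time on reward trials minus response time on non-reward trials, so that uniform or practice-related speeding does not count as benefit.
2. Reconcile Aim 2 with section 1.1 by choosing one of three positions: smaller reward-related speeding, as the stated model implies; acceleration as an explicit exception, with its rationale given and section 1.1 amended to match; or no specified direction for the MID, with the result reported two-sided and not scored as benefit or harm.
3. As minor clean-up, delete reward learning or define its MID variable, since the MID descriptions in sections 3.2, 6 and 7.2 give none. Express delay-discounting benefit as lower k, which section 6 names as the primary outcome.

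The cost is one or two sentences in section 7.2, and in section 1.1 if the exception is chosen, plus the clean-up edits. Data collection, models and sample size stay as they are.

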5.3 Method for Assigning Subjects to Treatment Groups

All subjects will receive the same drug protocol in a double-blind, cross over fashion. The study biostatistician will create a randomization table. Subjects will be randomized into two arms by permuted block of small size 2 with 1:1 ratio and maximum imbalance of 1. We will also restrict E2-P4 group to have the n = 8 and P4-E2 to have n=7 because the response from E2-P4 group is the primary phase of interest. The pre-generated randomization sequence will be uploaded to REDCap, with assignment group information coded. REDCap will randomly assign a possible number from table when a subject is entered. Study personnel will only receive that randomization number and will not receive information on the coded assignment group, so not only will they not know what group a subject is in, but they won't know which subjects have been similarly assigned. We will

not store any information on what assignment groups codes actually correspond to in REDCap, further ensuring that randomization remains concealed.

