Addback. After 6-weeks of Lupron-alone treatment (i.e., hypogonadism), physiological levels of E2 or P4 will be attained via oral micronized E2 (2mg b.i.d) or P4 (200mg b.i.d), respectively (along with continued Lupron administration), with a 2-week washout period in-between. Placebo pills continue during the washout. Each addback phase will be 2-weeks (compared with 4-weeks) as previous studies using this experimental design have shown significant symptom change can be obtained within 2-weeks.⁸⁷ Subjects will be randomized to receive E2 followed by P4 or P4 followed by E2. The study biostatistician will create a randomization table and study investigators will be blinded to the randomization order. End-of-phase assessments will occur at the end of E2 and P4 addback (T3/T4).

Once medication administration begins, subjects will be instructed to take pills twice daily, at approximately the same time each day. To improve medication compliance, we will recommend subjects schedule a daily reminder on their phone to take the study medication each day. The daily assessments will also ask participant’s whether they took the study medication each day.

Clinical Assessments. Measures used to obtain primary outcomes and monitor subject safety are shown in **Table 4**. Study visits will occur every 2-weeks. Participants will attend end-of-phase assessments at the end of each hormone phase as well as check-in visits to monitor symptoms. There will be an equal number of end-of-phase assessments and check-in visits (3 each) during the hormone challenge. All study measures are empirically valid and reliable.

Clinical Interviews

- a) **SCID-5:** Structured Clinical Interview for DSM-5¹⁸¹ will be administered by trained study staff at T0, and supervised by [name], to confirm eligibility and BN diagnosis. Based on DSM-5 criteria, the interview guides trained interviewers in determining whether a psychiatric diagnosis is present or absent.

Self-report Questionnaires

Self-report questionnaires will be completed through secure, encrypted, online survey (i.e., Qualtrics), and scored by standard conventions. During the reproductive hormone challenge, (i.e., T1-T4) self-report questionnaires will be modified to represent symptomatology over the previous week only, in order to capture the period of time with maximal or minimal pathology during each hormone manipulation phase.

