7.1 Sample Size Determination

This is a pilot study to obtain pilot data for larger studies. Previous observational studies in humans suggest at least a moderate effect of ovarian hormones on binge eating with an effect size approximating $d = 1.5$,^{5, 196, 197} including [name] pilot work described above. Additionally, [name] pilot work of E2 treatment in midlife women indicates $d = 2.3$ for the effect of E2 replacement decreasing appetite in women with and without major depression whereas other published work showed $d = 1.51$ for the effect of Lupron on decreasing food cravings in women with PMS.⁸⁷ Because we are directly manipulating ovarian hormones with an experimental design, which removes other potential confounds found in observational studies, we expect that the effect sizes from observational studies are an underestimate.

According to a power estimation for Aims 1 and 2, with a projected sample of $n = 15$, an effect size of .77 is required to detect a treatment difference at a two-sided .05 significance level at 80% power (calculated based off of projected sample size and desired power). Additionally, based on $n = 15$ and estimated effect size of 1.5 for E2 on binge eating (the average effect size observed in previous studies),^{5, 196, 197} a power estimation for Aim 1 (our primary aim) estimates our power at significance of .05 is $> 90\%$. Thus, despite the smaller sample size of this pilot study, power analyses indicate we should have sufficient power based on hypothesized effect sizes (which are empirically based) for E2 on binge eating.

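### Aim 3 correlates baseline-to-E2 changes across all women without conditioning on randomised order, so an order difference in both change scores would bias the pooled correlation

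*Combined protocol and SAP*

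**What the plan says.** Section 6 (Addback) states: "Subjects will be randomized to receive E2 followed by P4 or P4 followed by E2". Section 5.3 fixes the split: "We will also restrict E2-P4 group to have the n = 8 and P4-E2 to have n=7".

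Aim 3 in section 7.2 takes, for each woman, the change from baseline (T1) to E2 addback in the EPSI binge-eating score and in two self-report reward scales: BIS/BAS reward responsiveness and SPSRQ reward sensitivity. It then says: "A Pearson correlation will then be examined between binge eating and reward response change scores". There is no sequence term, stratification or partial correlation.

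For Aims 1 and 2 the same section lists "Independent variables: Treatment sequence, treatment condition, and selected covariates", with sequence as a fixed effect in a main-effects mixed model.

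The general text of section 7.2 puts the unadjusted analysis first and allows optional covariates, but sequence is not among its examples. The sensitivity paragraph covers modelling assumptions only in general terms.

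**The concern.** The change being correlated does not cover the same experience in the two orders. In the E2-P4 order it ends after six weeks of Lupron alone and two weeks of E2. In the P4-E2 order it ends four weeks later, after two weeks of P4, a two-week placebo washout and continued Lupron. By the visit schedule and Table 4, the E2 visit is the fifth administration of the self-report scales counted from T1 in one order and the seventh in the other.

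If any of this moves the mean binge change and the mean reward change between orders, the difference between two group means enters the pooled correlation as though it were an association between the two changes. Same-direction shifts push r upwards. Opposite shifts push it downwards and can hide a real positive link. Aim 3 is the only unconditional test relating reward change to binge change, and the pilot is meant to guide larger mechanistic trials, so a mixed r would be a poor guide. The Benjamini-Hochberg correction in section 7.2 does not remove a bias of this kind.

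**Working it through.** **Inputs from the documents**
- n = 15, split 8 and 7 (section 5.3).
- Two-sided .05 (section 7.1).
- Timing (sections 5.2 and 6): T2 at week 6. The first addback ends at 6 + 2 = week 8 (T3). The second ends at 8 + 2 (washout) + 2 = week 12 (T4).

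**Assumption.** The difference between orders in each change score, in within-order SDs, is not given in the documents. I take 0 to 1.5 SD.

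**The plan's own figure.** Section 7.1 says "an effect size of .77 is required to detect a treatment difference at a two-sided .05 significance level at 80% power". A paired t-test with n = 15 (14 df) gives a detectable effect of 0.778, and power of 79.2% at 0.77, so the figure reproduces. It is introduced with "According to a power estimation for Aims 1 and 2"; no power or precision is stated for the Aim 3 correlation.

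**Bias formula.** Let r_w be the correlation within an order, dx and dy the order differences in the two change scores, and pq = (8/15)(7/15) = 0.2489. Then

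pooled r = (r_w + pq·dx·dy) / √[(1 + pq·dx²)(1 + pq·dy²)].

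No true link (r_w = 0), same-direction shifts:
- 0.5 SD: 0.0622/1.0622 = .06
- 1 SD: 0.2489/1.2489 = .20
- 1.5 SD: 0.5600/1.5600 = .36

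True r_w = .65:
- opposite 0.5 SD: (.65 − 0.0622)/1.0622 = .55
- opposite 1 SD: (.65 − 0.2489)/1.2489 = .32
- 1 SD in one measure only: .65/√1.2489 = .58

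**Rejection rates.** I simulated 200,000 bivariate-normal trials of 8 + 7 per setting. The raw Pearson test has 13 df (critical |r| .514). The partial correlation given sequence has 12 df (critical |r| .532).

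| True r_w | Shift (binge, reward) | Raw r rejects | Partial r rejects |
|---|---|---|---|
| 0 | none | 5.0% | 5% |
| 0 | 0.5, 0.5 | 5.6% | 5% |
| 0 | 1, 1 | 11% | 5% |
| 0 | 1.5, 1.5 | 28% | 5% |
| 0 | 1, 0 | 5.0% | 5% |
| .65 | none | 79.6% | 76% |
| .65 | 0.5, −0.5 | 59% | 76% |
| .65 | 1, −1 | 16% | 76% |
| .65 | 1, 0 | 65% | 76% |

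The false-positive figures at 0.5 SD vary between about 5.4% and 5.7% from run to run.

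**Why the sequence term in Aims 1 and 2 is not a model for this.** A sequence main effect is a constant level difference between orders at every visit. Subtracting T1 from the E2 visit within each woman already removes it. A difference between orders in the change itself is a period or sequence-by-condition effect, and the main-effects models of Aims 1 and 2 contain neither.

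**Precision.** By Fisher's z with one conditioning variable, the standard error is 1/√(15 − 3 − 1) = 0.302. An observed partial r of .65 (z = 0.775) has a 95% interval of 0.775 ± 0.591 on the z scale, or .18 to .88.

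**The case against.** The strongest reply is that nothing shows the orders will differ. Every shift size is assumed. At 0.5 SD in both measures the false-positive rate barely moves. The 11% and 28% figures need order effects of 1 to 1.5 SD, in the same direction, in both scores. At 0.77 SD, numerically the effect the trial is sized to detect (the SD units are not identical), the rate is only 7.6%. A shift in one measure alone creates no false link. The aim is worded as exploration in a 15-woman proof-of-concept study, and imprecision is the larger problem whichever correlation is used. The optional covariates and generic sensitivity analyses would also permit a sequence-adjusted check. All of this stands, except that permission is not a plan: sequence is nowhere named for Aim 3.

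Four stronger readings are tempting, and the documents do not support them.
- A reader might infer that Aims 1 and 2 are protected and Aim 3 alone is not. Their sequence main effect does not address an order difference in change scores.
- A reader might take section 1.3, which says P4 may antagonise E2, as evidence of carry-over. That statement summarises preclinical work, and section 1.1 describes antagonism when both hormones are high. Here they are given separately with a two-week washout, and nothing cited shows an effect of P4 two weeks after it stops.
- A reader might see the problem as contamination of a link within women. With one change score per woman, both the raw and the partial correlation are between-women quantities.
- A reader might treat Aim 3 as the trial's main mechanistic evidence. It has stated null and alternative hypotheses, but it is exploratory, and the mediation step depends on Aims 1 and 2 rather than on it.

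**Conclusion.** The point holds as a conditional one. The raw pooled correlation is open to bias from order differences in the change scores, and the plan does not condition on the order it randomises. A false link requires shifts in both measures and becomes material at about 1 SD. Loss of a true link starts sooner: at r = .65, opposite shifts of 0.5 SD cost about 20 points of power (79.6% to 59%), and a 1-SD shift in one measure costs about 15 (79.6% to 65%). These figures assume bivariate-normal changes, equal variances, a common slope in both orders and no dropout. The shift sizes are mine, not the documents'. The change is worth making because it is cheap, not because bias has been shown to be likely. It has no bearing on the Aim 1 primary analysis.

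**What to change.** In section 7.2, Aim 3, state that the estimate is the partial correlation of the binge-eating and reward change scores given treatment sequence (E2-P4 or P4-E2), tested on n − 3 = 12 df and reported with a 95% confidence interval. Report the raw Pearson r beside it, and show a scatterplot with points marked by sequence. Add that the partial correlation assumes one slope for both orders, which 8 and 7 women cannot usefully test.

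The cost is a sentence or two of text and one degree of freedom. If the orders do not differ, power at r = .65 goes from 79.6% to about 76%. No new data or visits are needed.
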